5.2 Schedule of Study Procedures and Assessments

The table below summarizes the study assessments and procedures.

Table 1. Study Assessments and Procedures

Procedure		Baseline	Wk 1	Wk 3	Wk 6	Wk 9	Wk 12	Wk 15	Wk 18	Wk 21	Wk 24	Wk 25
Call #		1	2	3	4			5	6	7		8
Visit #		1					2				3	
Informed Consent												
Clinical Assessments												
Medical Hx		x										
Symptoms assessment			x	x	x	x	x	x	x	x	x	x
Medications		x	x	x	x	x	x	x	x	x	x	
Vital Signs		x					x				x	
Physical Exam		x					x				x	
WHO Functional Class		x					x				x	
Testing												
Urine collection		x									x	
Phlebotomy		x									x	
6MWTD		x					x				x	
ECG		x					x				x	
SF-36 and emphasis-10		x					x				x	
Imaging												
Echocardiogram		x					x				x	
ESR-specific PET study		x									x	
Study Procedures												
Dispense study drug or placebo		x					x					
Review adverse events			x	x	x	x	x	x	x	x	x	x
Review study drug/placebo diary & compliance			x	x	x	x	x	x	x	x	x	

5.3 Subjects' retention and drug compliance

We will enforce subject retention in several ways. We will record extensive contact information for each subject at their enrollment in the trial. This will include home, work, and cellular telephone numbers. The research coordinator will call before each study visit to remind the subject to attend. Subjects will be reimbursed for time at the clinic for research procedures and reasonable travel expenses necessary for their participation in the study. Subjects will receive \$200 for the Baseline Visit and \$250 for the remaining study visits (week 12 and week 24).

The research coordinator and physician will explain the importance of compliance with the study protocol at each subject contact. If a subject fails to comply with a study visit, the coordinator will contact him or her by telephone. If this fails, the coordinator will send two letters, one week apart, to request follow-up.

We have considered how to minimize difficulties with adherence to the study drug (or placebo). We will strongly emphasize the importance of complying with the study drug treatment. Nonetheless, we will perform pill counts at visits and record episodes when medication is withheld for any reason. If a subject wishes to drop-out from the treatment phase of the study or has a serious adverse event (SAE) (whether related to study drugs or not), we will continue to follow-up with the subject for study assessments to assist with safety monitoring and to avoid the problems introduced by missing data. The inclusion of such follow-up data will allow for analysis by intention-to-treat.

If a subject is withdrawn from the treatment portion of the study for any reason, the subject will be strongly encouraged to continue with the remainder of the study assessments, as scheduled.

Chapter 6. Assessment of Efficacy and Outcome Measures

6.1 Assessments of efficacy

Primary

To evaluate the change (Week 0 to 24) in tricuspid annular plane systolic excursion (TAPSE), determined by transthoracic echocardiography (TTE), in tamoxifen vs. placebo.

Secondary

There are several secondary objectives of this study. They include:

- To evaluate the change (Week 0 to 24) in other echocardiographic metrics of right ventricular function determined by TTE in tamoxifen vs. placebo.
- To evaluate the effect of tamoxifen vs. placebo on TAPSE at Week 12 by TTE.
- To evaluate the effect of tamoxifen vs. placebo on other echocardiographic metrics of right ventricular function at Week 12 by TTE.
- To evaluate the effect of tamoxifen vs. placebo on 6MWD at Week 12 and Week 24.
- To evaluate the effect of tamoxifen vs. placebo on the SF36 and emPHasis-10 at Week 12 and 24.
- To evaluate the effect of tamoxifen vs. placebo on plasma BNP level at Week 24.
- To evaluate the effect of tamoxifen vs. placebo on metabolism-related biomarkers at Week 24.
- To evaluate the change (Week 0 to 24) in sex hormone, and sex hormone metabolite, levels in the urine and plasma (Week 0 to 24) in tamoxifen vs. placebo.
- To evaluate the change (Week 0 to 24) in estrogen receptor (ESR) density, as determined by ¹⁸FES PET, in tamoxifen vs. placebo.
- To evaluate the safety and side effects associated with tamoxifen administration in subjects with PAH.

6.2 Information on select secondary outcome measures

6.2.1 ESR-specific PET tracer to determine lung ESR density.

In vivo evaluation of ESR expression using ¹⁸F-FES uptake by positron emission tomography (PET) is an established non-invasive, real-time measure of the activity of ESR modulators such as tamoxifen⁴⁸, which has been used extensively by Co-I [name] and colleagues¹¹. In fact, ¹⁸F-FES has been evaluated in numerous cancer clinical studies as a promising method for quantifying in vivo ESR expression, predicting response to hormone therapy, and evaluating effective ESR blockade. It correlates well with traditional in vitro immunohistochemical methods and has shown potential for evaluating, and predicting, an individual's drug response⁴⁸. In preliminary studies, we evaluated lung ESR density in females pre- and during therapy with tamoxifen for breast cancer. Women (n=7) were evaluated at baseline, with standardized uptake values (SUVs) determined in the total lung and at standardized regions of interest (ROI, m³). Baseline lung SUV levels were similar among the women (0.95 ± 0.17). Three women

were evaluated after 6 weeks or longer of tamoxifen therapy, with a reduction in lung SUV levels demonstrating suppression of lung FES uptake due to ESR antagonism by tamoxifen. Thus, ¹⁸F-FES PET not only has the ability to quantify lung ESR expression, it demonstrates effective ESR blockade due to tamoxifen exposure. As in cancers, this may help to identify patients with a high or low burden of ESR expression in the lung *a priori*, providing the opportunity to more precisely select patients for tamoxifen therapy.

6.2.3 WHO functional class

The WHO functional classification for PAH has been modified from the well-known New York Heart Association functional classification. This functional classification is based on symptoms, with Class I being defined by no symptoms, Class II as having mild limitation in physical activity, Class III as having markedly limited physical activity and Class IV as being unable to perform any physical activity. The WHO functional class will be assessed at every visit.

Chapter 7. Statistical Considerations

7.1 Study design

Single-center, randomized, double-blind, placebo-controlled Phase II study of 24 subjects with PAH. Eligible subjects will be randomized to treatment with a 1:1 ratio using a permuted-block randomization algorithm.

All subjects will also be treated with background standard of care therapy at the discretion of their PAH care physician.

7.2 Disposition of subjects and baseline comparisons

Summaries of all subjects screened, recruited, and randomized and the number who complete visits will be provided, according to guidelines. The treatment groups will be compared at baseline with respect to demographics and baseline measurements related to efficacy and safety without formal statistical testing.

7.3 Statistical procedures

7.3.1 Data analysis

The intent-to-treat analysis will include all randomized subjects. Hypothesis testing will use two-sided $\alpha = 0.05$ without correction for multiplicity.

The primary and secondary endpoints are described in Chapter 6.

Continuous endpoints will be analyzed using the Wilcoxon Rank Sum test to assess between treatment arms difference and using the signed rank test for within-group change from baseline. For binary endpoints, Fischer's exact test will be used to assess between treatment arms difference.

For the primary endpoint, TAPSE, an exploratory analysis using mixed effects model will be conducted to assess the time trend and treatment effect (tamoxifen vs placebo). The mixed effects models will have a random subject effect and we will use an autoregressive model of order 1 (AR1) or other plausible covariance structures for the error covariance. In addition, the association between baseline (pre-tamoxifen or placebo) lung ESR density and response to treatment quantified by TAPSE and 6MWT distance will also be evaluated using the mixed effects models. These analyses will be of particular interest since they will help us *a priori* to identify patients who will be most likely responders to tamoxifen in the next-phase studies should this proof-of-concept study be a success.

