Study Design	Single-center, randomized, double-blind, placebo-controlled Phase II study of 24 subjects with PAH. Eligible subjects will be randomized to treatment with a 1:1 ratio using a permuted-block randomization algorithm. All subjects will also be treated with background standard of care therapy at the discretion of their PAH care physician.
Number of patients	24 patients; 12 will be allocated to tamoxifen and 12 will be allocated to placebo.
Duration of Therapy	24 weeks
Study Drug	
Tamoxifen: 20 mg
 
Tamoxifen is an oral selective estrogen receptor modulator (SERM).

Study Observations	
 • Subjects will be evaluated in person at baseline, 12 weeks, and 24 weeks. • Subjects will have telephone follow-up at 1, 3, 6, 9, 15, 18, 21 weeks. • Laboratory tests including a complete blood count, routine chemistry tests (creatinine and electrolytes), liver function tests, coagulation studies, calcium, and • BNP levels and other biomarkers will be assessed at baseline and 24 months. • Subjects will undergo a six minute walk test at baseline, 12, and 24 weeks.

	
 Subjects will have a transthoracic echocardiogram at baseline, 12 and 24 weeks. Estrogen receptor (ESR) density, as determined by ¹⁸FES PET, will be assessed at baseline and 24 weeks. Quality of life will be assessed by SF36 and emPHasis-10 at baseline, 12 and 24 weeks.
Safety Assessments	Analyses will be performed for all patients having received at least one dose of study drug. General safety endpoints such as adverse events will be reported according to FDA guidelines.
Sample Size and Power	A total of 24 subjects will be enrolled with 1:1 randomization to either tamoxifen or placebo. Should a randomized patient drop-out before 24 weeks of treatment, that patient will be replaced to ensure at least 12 patients complete 24 weeks of treatment in each arm. For the primary study endpoint of TAPSE, we will have 71% and 88% power, respectively, to detect a drop from 1.80 cm or 1.85 cm at baseline to 1.60 cm (the risk boundary for RV dysfunction) using an SD for the within-subject difference of 0.25 cm.

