2.1 Objective

To evaluate the change (Week 0 to 24) in tricuspid annular plane systolic excursion (TAPSE), determined by transthoracic echocardiography (TTE), in tamoxifen versus placebo.

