7.4 Sample size and power calculations

A total of 24 subjects will be enrolled with 1:1 randomization to either tamoxifen or placebo. Should a randomized patient drop-out before 24 weeks of treatment, that patient will be replaced to ensure at least 12 patients complete 24 weeks of treatment in each arm. For the primary study endpoint of TAPSE, we will have 71% and 88% power, respectively, to detect a drop from 1.80 cm or 1.85 cm at baseline to 1.60 cm (the risk boundary for RV dysfunction) using an SD for the within-subject difference of 0.25 cm.

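### The primary TAPSE comparison uses baseline only by subtraction; a pre-specified ANCOVA is a cheap possible gain in precision, not the repair of an error, and its size rests on figures the protocol does not give

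*Combined protocol and SAP*

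**What the plan says.** Section 2.1 states what the trial chiefly sets out to do: "To evaluate the change (Week 0 to 24) in tricuspid annular plane systolic excursion (TAPSE), determined by transthoracic echocardiography (TTE), in tamoxifen versus placebo". Section 6.1 repeats it as the primary efficacy assessment. Section 7.3.1 points there ("The primary and secondary endpoints are described in Chapter 6") and then gives one rule for all continuous endpoints: "Continuous endpoints will be analyzed using the Wilcoxon Rank Sum test to assess between treatment arms difference". The Data Analysis row of the Abstract says the same. No covariate is named for this comparison, and no effect estimate or confidence interval.

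Baseline TAPSE will be available: "Subjects will have a transthoracic echocardiogram at baseline, 12 and 24 weeks" (Abstract, Study Observations; also Section 5.1.2 and Table 1). Section 7.2 uses baseline data descriptively: "The treatment groups will be compared at baseline with respect to demographics and baseline measurements related to efficacy and safety without formal statistical testing".

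Section 7.3.1 also plans mixed models. One is an exploratory model of TAPSE for time trend and treatment effect; the other relates baseline lung receptor density to response. Neither replaces the rank-sum test, and neither names baseline TAPSE as a covariate.

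**The concern.** Subtracting baseline fixes the slope of Week 24 TAPSE on baseline TAPSE at 1. ANCOVA estimates that slope. If the true slope is well below 1, the change score carries baseline noise that ANCOVA would remove, at no cost in recruitment or data collection.

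With 12 per arm, precision is the main limit on what the trial can show. Section 2.2 also lists, as an aim, finding the sample size for a larger study. A rank-sum p-value serves that aim poorly. An adjusted difference in centimetres, with its interval and residual SD, serves it directly, whatever rho is.

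**Working it through.** **Inputs from the documents.** 12 per arm, and change SD 0.25 cm ("using an SD for the within-subject difference of 0.25 cm"), from Section 7.4; two-sided alpha 0.05, from Section 7.3.1.

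**Assumed inputs.** Rho; k = Week 24 SD / baseline SD; and a between-arm difference of 0.20 cm. Section 7.4 describes within-arm drops ("to detect a drop from 1.80 cm or 1.85 cm at baseline to 1.60 cm", so 0.20 and 0.25 cm), not between-arm differences.

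**The plan's own figure.** A one-arm paired t-test with n = 12 and SD 0.25 cm gives 71.4% and 88.3%, matching the stated 71% and 88%. A two-arm t-test on change with the same inputs gives 46.6% and 64.9%. That mismatch is a separate point.

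**Planned test.** The exact 12 v 12 rank-sum test rejects at U ≤ 37, attained level 0.0449. Simulated power at 0.20 cm is about 43% (normal data, any rho).

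**T-test on change.** SE = 0.25 × √(2/12) = 0.102 cm; noncentrality 0.20/0.102 = 1.96; 22 df; power 46.6%, or 44.6% at level 0.0449. So moving to a parametric test adds about 4 points before any adjustment, and about 2 of those only reflect the rank-sum test's discrete level.

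**ANCOVA.** The variance ratio to the change score is

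V = 1.05 × k²(1 − rho²) / (1 + k² − 2k·rho),

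where 1.05 = 1 + 1/20 is the cost of estimating the slope from 24 subjects. With k = 1 this becomes 1.05 × (1 + rho)/2. Power uses a noncentral t with 21 df and SE = 0.102 × √V. Example, k = 1 and rho 0.5: V = 1.05 × 0.75 = 0.788; SE = 0.0906; noncentrality 2.21; power 55.8%.

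ANCOVA at 0.20 cm, normal data (V, then power):

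| rho | k = 1 | k = 1.2 | k = 0.8 |
|---|---|---|---|
| 0.3 | 0.683, 61.9% | 0.800, 55.2% | 0.527, 73.0% |
| 0.5 | 0.788, 55.8% | 0.915, 49.8% | 0.600, 67.5% |
| 0.7 | 0.893, 50.8% | 1.015, 45.9% | 0.659, 63.4% |
| 0.8 | 0.945, 48.5% | 1.047, 44.7% | 0.672, 62.6% |
| 0.9 | 0.998, 46.5% | 1.026, 45.5% | 0.638, 64.8% |

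Simulation agrees with these values, with ANCOVA type I error near 5%.

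**Reading the table.**
- Equal SDs: adjustment alone (ANCOVA minus 46.6%) adds about 15, 9, 4, 2 and 0 points. Break-even against the t-test on change is rho = 2/1.05 − 1 = 0.905. In variance terms, 12 per arm acts like 12/V = 17.6, 15.2, 13.4, 12.7 and 12.0 per arm.
- Week 24 SD 20% larger: V exceeds 1 at rho 0.7, 0.8 and 0.9, so ANCOVA is slightly less precise than a t-test on change there. It still exceeds the 43% of the rank-sum test.
- Week 24 SD 20% smaller: ANCOVA gains throughout, 63 to 73%.

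**Heavy tails (t, 4 df), simulated at 0.20 cm.** Equal SDs: rank-sum 56% v ANCOVA 68, 63, 58, 56 and 53%, so the lead ends near rho 0.8. Week 24 SD 20% larger: ANCOVA trails by about 3 to 4 points at rho 0.7 and above (at 0.7, 52.8% v 55.5%).

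**The case against.** Four objections carry weight.

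1. A rank test with 12 per arm is a defensible robust choice, and ANCOVA's linearity and normality are hard to check with 24 subjects. This stands, and it is why the rank-sum test should stay as the sensitivity analysis.

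2. The large gains need a between-subject TAPSE SD no larger than the change SD: with equal SDs, rho 0.3 and 0.5 imply visit SDs of 0.21 and 0.25 cm, against 0.40 cm at rho 0.8. Section 3.2.1 admits WHO Class I to III with no TAPSE limit, which sits poorly with so narrow a spread. Background therapy is unrestricted (Section 4.4) and subjects who worsen continue (Section 9.4.8), so a larger Week 24 SD is possible. The documents do not settle either matter.

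3. The exploratory mixed model could recover much the same adjustment if, for example, it assumed a common baseline mean. Its parameterisation is not stated, and it remains exploratory, so the primary test is unchanged.

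4. The change comes late: version 5.0 is dated 2020 and the latest IRB approval August 2024. The documents do not show whether unblinding has occurred, so the proposal must be conditional on that.

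Three stronger readings are tempting and are not supported. A reader might infer that the planned test is invalid or biased. It is not: it holds its type I error, and the shift from a chance baseline imbalance averages zero over repeated trials. A reader might infer that ANCOVA wins whenever rho is below about 0.8. As the k = 1.2 column shows, no such threshold holds without equal visit SDs. A reader might infer that ANCOVA repairs the stated power. With equal SDs it reaches at most 61.9% and 80.7% (at rho 0.3) for 0.20 and 0.25 cm, against the stated 71% and 88%.

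**Conclusion.** The point holds as an inexpensive improvement, not as an error in the plan. On normal data ANCOVA had more power than the planned rank-sum test at every assumed rho and SD ratio shown. The margin at 0.20 cm runs from about 2 points (Week 24 SD 20% larger, rho 0.8) through 4 to 19 points (equal SDs) to about 30 (Week 24 SD 20% smaller, rho 0.3). About 4 points of each margin are owed to the parametric test. With heavy tails the advantage disappears near rho 0.8, and it reverses by 3 to 4 points at rho 0.7 and above if Week 24 spread is also 20% larger. All of this is conditional on rho, the SD ratio and the between-arm difference, none of which the documents give; only the change SD and the sample size are theirs.

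**What to change.** By protocol amendment before unblinding, pre-specify ANCOVA of Week 24 TAPSE on treatment and baseline TAPSE as the primary analysis, and report the adjusted difference with its 95% CI. Keep the rank-sum test on the Week 0 to 24 change as the sensitivity analysis. Limit the change to TAPSE. State in Section 7.3.1 that the gain depends on rho and on the ratio of the visit SDs.

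Blinded pooled data can inform the decision only roughly. With 24 subjects, an observed rho of 0.8 has an approximate 95% interval of 0.59 to 0.91, and 0.7 has 0.41 to 0.86 (Fisher z, standard error 1/√21).

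Costs: an amendment through the IRB (Section 9.9); one degree of freedom and about 5% variance inflation; linearity and normality assumptions that are hard to verify at this size; and a possible small loss of power with heavy tails or a larger Week 24 spread. No new data are needed. If the primary test can no longer be changed, a smaller step is to state how the exploratory mixed model handles baseline TAPSE.

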7.3.2 Univariate analysis

We will characterize subjects with regard to baseline and follow-up TAPSE and other endpoints. We will summarize demographics and other predictors of clinical status. Continuous variables will be summarized by the mean, median, standard deviation, and

range, as appropriate. We will use contingency tables for discrete and dichotomous variables.

7.3.3 Missing data and dropouts

We will attempt to minimize missing data, however we have planned for its occurrence. For subjects lost to follow-up, we will use all of the information available until the end of follow-up.

This protocol will continue to follow subjects and perform test procedures as prescribed even if a subject drops-out from the therapeutic portion of the study. That is, if a subject decides that he/she does not wish to continue taking the study drug(s), the subject will stop the investigational treatment, but will still be strongly encouraged to continue to follow-up with the study personnel for all scheduled study procedures, so that missing data (and assumptions regarding these data) will be minimized.

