7.6 Protocol violations

Serious protocol violations such as discontinuation of experimental treatment unrelated to AEs will be carefully recorded and regularly reviewed by the lead study investigators Drs. [name] and [name]. Remedial changes in procedure will be recommended where feasible to reduce the incidence of such violations. The causes and circumstances of all violations will be documented where known for purposes of future secondary analyses and interpretation. Because all primary analyses will be intent-to-treat, it is essential that violations be kept to a minimum especially where it is possible to influence their rate of occurrence.

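### Does the lack of a rule for patients without a Week 24 echo undermine the intention-to-treat primary analysis?

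*Combined protocol and SAP*

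**What the plan says.** Section 6.1 makes TAPSE change from Week 0 to Week 24 the primary measure. Section 7.3.1 sets the population, "The intent-to-treat analysis will include all randomized subjects", and the test, "Continuous endpoints will be analyzed using the Wilcoxon Rank Sum test to assess between treatment arms difference". Section 7.6 repeats the commitment: "Because all primary analyses will be intent-to-treat".

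On missing values, section 7.3.3 states: "For subjects lost to follow-up, we will use all of the information available until the end of follow-up". The rest of that section, with sections 5.3 and 9.4.8, keeps patients who stop study drug in the scheduled assessments. Section 7.4 adds replacement of a patient who drops out before 24 weeks: "that patient will be replaced to ensure at least 12 patients complete 24 weeks of treatment in each arm".

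The echo schedule in the Abstract includes an intermediate visit: "Subjects will have a transthoracic echocardiogram at baseline, 12 and 24 weeks". A model that could use the Week 12 value is planned, but in a supporting role: "For the primary endpoint, TAPSE, an exploratory analysis using mixed effects model will be conducted".

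No section says how a patient with no Week 24 TAPSE enters the rank-sum test, or how death or transplant is treated in it.

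**The concern.** Read literally, the commitments cannot all be met. A rank-sum test on a change score needs a value or an assigned rank for every patient, so including everyone randomized is impossible once one Week 24 echo is missing. The sentence in 7.3.3 could mean omission, carrying Week 12 forward (impossible for anyone lost before Week 12), or reliance on the mixed model, which is exploratory.

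The missing value may also be informative. The Narrative Abstract describes right heart failure progressing to death or transplant, and section 1.2 ties right ventricular function to survival. If poor outcomes vanish from the tamoxifen arm, the comparison tilts towards benefit; if they vanish from placebo, it tilts towards no effect. With 12 per arm one patient carries weight, and replacement restores the number of completers without recovering the lost outcome. A rule chosen after unblinding could be chosen with the result in view.

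**Working it through.** **1. The plan's own figure.** Section 7.4 gives 71% and 88% power for drops of 0.20 and 0.25 cm with a within-subject SD of 0.25 cm. A paired t-test in 12 patients (two-sided 0.05) has noncentrality (0.20/0.25)√12 = 2.77 and (0.25/0.25)√12 = 3.46. Power is then 71.4% and 88.3%, so the figures reproduce. They describe a within-arm change in 12 complete pairs, with no allowance for missing values. For the between-arm rank-sum test at 12 v 12, simulation gives about 43% at 0.20 cm. That is the reference below; the difference from 71% is a separate matter.

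**2. How often a value is lost to death or transplant.** Section 1.1 gives about 60% event-free at three years. At constant hazard, 24-week risk = 1 − 0.6^(24/156.5) = 7.5%. Class IV and acutely ill patients are excluded (section 3.2.2), so 2–4% per arm is assumed instead; this is not a document figure.
- At least one loss among 24: 1 − 0.98^24 = 38%; 1 − 0.96^24 = 62%.
- Exactly one, in the tamoxifen arm, with none on placebo: 12 × 0.02 × 0.98^23 = 15%; 12 × 0.04 × 0.96^23 = 19%. The mirror case on placebo is equally likely when loss rates are equal.

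**3. What omission does on average.** Simulation inputs: 12 per arm, SD of change 0.25 cm, exact two-sided rank-sum at 0.05, 40,000 trials, equal loss of 2% or 4%, correlation r between loss and TAPSE change. Simulation error is √(0.43 × 0.57/40,000) = 0.25 points for power and √(0.022 × 0.978/40,000) = 0.07 points for false benefit.

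| Setting | Omission | No loss |
|---|---|---|
| No effect, r = 0 to 1: estimate | within 0.001 cm of 0 | 0 |
| No effect, r = 0 to 1: false benefit | 2.2–2.3% | 2.2% |
| 0.20 cm, loss unrelated to treatment: power | 41.1–42.5% | 42.8% |
| 0.20 cm, loss depends on treated change (r = 0.5 to 1): power | 38.9–41.3% | 42.8% |
| Same: estimate | 0.182–0.196 cm | 0.20 cm |

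These runs do not include replacement. Adding it (r = 0.5, loss unrelated to treatment) gives 43–44% power, so that power cost disappears.

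**4. What one loss in one arm does.** For scale, the standard error of a difference in means is 0.25 × √(2/12) = 0.102 cm.
- One tamoxifen loss, no effect: +0.017 cm and 3.3% false benefit at r = 0.5; +0.037 cm and 5.0% if it is the worst patient, which is 0.037/0.102 = 0.36 standard errors. Replacing the worst patient still leaves +0.034 cm and 4.8%.
- One placebo loss, 0.20 cm effect: 0.182 cm and 35% power at r = 0.5; 0.163 cm and 33% if it is the worst patient (0.166 cm and 35% with replacement).

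**5. Imbalance caused by the drug.** Section 4.1 reports 9/455 v 3/455 thromboembolic events, a difference of 6/455 = 1.3%, in another population and against another drug. Treating every event as a loss gives 3.3% v 2%: +0.003 to +0.007 cm and 2.4% false benefit. Even 7.5% v 2% gives +0.012 to +0.026 cm and 2.8–3.5%.

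**6. What the main alternative does.** Worst ranks for each loss, 0.20 cm effect:
- Loss unrelated to treatment: 36.7–40.2% power, against 41.1–42.5% with omission.
- Loss depending on the treated change: 41.9–42.9%, against 38.9–41.3%.
- One tamoxifen death unrelated to TAPSE, none on placebo: 21%, against 41%. With no drug effect, the chance of a false harm signal rises from 2.2% to 3.8%.

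**7. How often the two rules disagree on significance.** In trials with at least one loss: 14–18% at 0.20 cm and 3–4% with no effect. Over all trials, at the outer limits: 0.384 × 0.138 = 5% to 0.625 × 0.183 = 11%, and 0.384 × 0.034 = 1% to 0.625 × 0.042 = 3%.

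**The case for a change.** The strongest case for a change is that the significance verdict can turn on an unwritten choice, possibly made after unblinding, and that writing it down costs nothing. Continued follow-up cannot produce an echo after death, replacement brings a new patient and not the lost outcome, and the trial is meant to inform a larger one.

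Much of this stands. The rule is absent, the intention-to-treat sentence promises more than the test can deliver, and a single informative loss in one arm would not be trivial.

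It does not follow that the plan needs altering. Disagreement between omission and worst ranks is not an error rate: one rule addresses TAPSE change, the other TAPSE combined with death or transplant, and such analyses will sometimes differ. Adopting worst ranks would change what the primary endpoint measures. It would also need a rule for ordering several events and another for a transplanted patient who does have a Week 24 echo. For every other missing value, where an assigned worst rank is harder to justify, the sensible handling is omission with the mixed model alongside, and the plan's methods already allow that. Adding a cross-reference, relabelling the mixed model or tabulating missing values would change no result.

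**Conclusion.** The concern identifies a real gap in specification, not a rule that gives a wrong answer, and no change to the plan follows. An analyst would rank the patients who have a Week 24 TAPSE, show the mixed model beside that result, and account for missing values by arm and reason. Settling this before unblinding is ordinary practice.

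Under equal loss of 2–4% per arm, that default leaves the false-benefit rate at 2.2–2.3% and takes power at 0.20 cm from about 43% to 39–42%. The larger effects, up to about 0.04 cm and 5.0% false benefit, need one loss in one arm who is also its worst patient; one tamoxifen loss with none on placebo occurs in 15–19% of trials even before that last condition. The substantive alternative loses power when events are unrelated to treatment and gains 1–4 points when they depend on the treated change, so the choice is a fair trade-off.

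This rests on the assumed 2–4% rate, normally distributed changes with SD 0.25 cm in each arm, and loss from death or transplant only. The documents give no rate for withdrawal or lost contact. A markedly higher or strongly one-sided loss would make the choice of rule matter more.
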